## 4.2 Rationale

### 4.2.1 Rationale for the Trial and Selected Subject Population

*Immune Checkpoint Therapy in Malignant Disease.* Cancer immunotherapy has been investigated as a viable anti-tumor therapy for several decades but only recently has been accepted as a pillar of cancer therapy . That the immune system is an effective treatment against hematologic malignancies is evidenced by the utilization of allogeneic stem cell transplantation, where graft versus lymphoma/leukemia effects result in valuable therapy. The

programmed death (PD-1) pathway is involved in potent inhibition of immune activation, especially through inhibition of effector T cell function. The PD-1 receptor is a transmembrane protein expressed on activated T cells and other immune cells. T cell exhaustion occurs when PD-1 ligands (PD-L1, PD-L2) activate their receptors, initiating an inhibitory signaling network that results in apoptosis of activated T cells. PD ligand expression is minimal in normal tissues, but markedly upregulated in acute inflammatory environments, implicating its role in peripheral tolerance. Recent pre-clinical and clinical studies suggest that the PD-1/PD-ligand pathway plays a pivotal role in tumor immune evasion, as PD-1 receptor and ligand expression is increased in several malignancies. Encouraging responses have been demonstrated in patients with advanced diseases treated with antibodies targeting PD-1 and PD-L1 leading to FDA approval of two antibodies against PD1 for the treatment of melanoma in 2014.

*PD-1 blockade for lymphoma.* Manipulation of the PD-1/PDL-1 pathway is of recent interest in patients with classical Hodgkin lymphoma (cHL) and several non-Hodgkin lymphomas (NHLs) including follicular lymphoma (FL) and diffuse large B-cell lymphoma (DLBCL). Indeed in cHL, two distinct phase 1 clinical trials evaluating single agent PD-1 blockade with a monoclonal antibody demonstrated impressive overall response rates (ORR) of 87% and 53% among patients with refractory cHL, of whom the majority failed autologous stem cell transplantation as well as brentuximab. Complete response (CR) rates were 17% and 20% in these studies. Data is also emerging regarding the clinical utility of immune checkpoint inhibition in NHL. We have recently demonstrated that in FL, PD-1 blockade in combination with anti-CD20 targeting agent rituximab was well tolerated and resulted in an ORR of 66% and CR in 52% of patients treated with this approach. A recent publication in *Blood* revealed that among patients with DLBCL, tumor biopsy expression of PD-L1 negatively impacted overall survival suggesting a potential role for the PD-1/PD-L1 pathway in this patient population.

Preliminary data from an ongoing trial evaluating PD-1 blockade in NHLs, however suggests that the full potential of immune checkpoint blockage will not be reached with anti-PD-1 monotherapy. In this study of 81 patients, including 31 and 23 patients with B-cell NHL and T-cell NHL respectively, the ORR was 26% among patients with B cell NHL and 17% among patients with T-cell NHL (Figure 3). The compete response rate was 10% among the B cell NHL subjects and 0% for those with T cell NHL. This suggests that effective cancer immunotherapy likely requires cooperation with other anti-tumor modalities for improved

efficacy. One potential combination strategy to augment response is external beam radiation therapy coupled with PD-1 blockade.

Tumor	OR, No. (%)	CR, No. (%)	PR, No. (%)	SD, No. (%)	Median PFS, Weeks (95% CI)
B-cell lymphoma (n = 31)	8 (26)	3 (10)	5 (16)	16 (52)	23 (7 to 44)
DLBCL (n = 11)	4 (36)	2 (18)	2 (18)	3 (27)	7 (6 to 29)
FL (n = 10)	4 (40)	1 (10)	3 (30)	6 (60)	NR (7 to NR)
Other B-cell lymphoma (n = 10)	0	0	0	7 (70)	11 (3 to 39)
T-cell lymphoma (n = 23)	4 (17)	0	4 (17)	10 (43)	10 (7 to 33)
MF (n = 13)	2 (15)	0	2 (15)	9 (69)	10 (7 to 35)
PTCL (n = 5)	2 (40)	0	2 (40)	0	14 (3 to NR)
Other CTCL (n = 3)	0	0	0	0	7 (6 to NR)
Other non-CTCL (n = 2)	0	0	0	1 (50)	10 (2 to 18)
Multiple myeloma (n = 27)	1 (4)	1 (4)*	0	17 (63)	10 (5 to 15)

Abbreviations: CR, complete response; CTCL, cutaneous T-cell lymphoma; DLBCL, diffuse large B-cell lymphoma; FL, follicular lymphoma; MF, mycosis fungoides; NR, not reported; OR, objective response; PFS, progression-free survival; PR, partial response; PTCL, peripheral T-cell lymphoma; SD, stable disease.

\*CR was obtained after radiotherapy. SD was the best response to nivolumab.

**Figure 3.** Efficacy Results from a Phase I, open-label study of patients with relapsed or refractory B cell lymphoma, T-cell lymphoma and multiple myeloma treated with anti-PD 1 monoclonal antibody nivolumab. (From Lesokhin AM, Ansell SM, Armand P. et al, Nivolumab in Patients With Relapsed or Refractory Hematologic Malignancy: Preliminary Results of a Phase Ib Study. J Clin Oncol. 2016 Aug 10;34(23):2698-704).

*Combination RT and immune checkpoint blockade.* The primary mechanism of radiation induced cancer cell death is via DNA damage. However, several studies suggest that the immune system contributes to the anti-neoplastic effects of radiation and is required for the full therapeutic effects of RT to be realized. In 1979 Stone and colleagues recognized that increased doses of radiation were required to control fibrosarcomas in animals that were immunosuppressed, as compared to animals treated with a crude bacterial preparation aimed at immune system stimulation. The abscopal effect describes a phenomenon where tumor regression occurs after RT within a non-irradiated tumor site. Pre-clinical work by Formenti and colleagues demonstrated that the ability of ionizing radiation to decrease tumor growth outside of the radiation field was immune mediated and T-cell dependent. To increase dendritic cell number, growth factor Flt3-Ligand was given to mice harboring a syngeneic mammary carcinoma on both flanks, after local RT to one tumor. Growth of the non-irradiated tumor was reduced by the combination of RT and Flt3-Ligand; while Flt3-ligand alone did not produce this effect without radiation. These effects were not present in T cell deficient nude mice. Furthermore, growth of a non-irradiated lymphoma in the same mice that harbored a treated mammary tumor was not impaired. The potential for radiation to partner with the immune system to create an *in vivo* vaccine was proposed in 2005 by Formenti and colleagues and has gained momentum recently as evidence emerges supporting this hypothesis.

Recent clinical and pre-clinical data suggests that EBRT induces a tumor specific immune response in irradiated and non-irradiated tumors that is mediated by PD-1 blockade.

While stereotactic ablative radiation doses have been used primarily to this effect in patients with known radio-resistant tumor histologies such as melanoma, lower radiation doses may have similar efficacy in patients with hematologic malignancies given the inherent radiosensitivity of these tumors. Utilization of lower doses also has the potential to decrease treatment related toxicity. Furthermore lower radiation doses may be more effective in preserving normal tissue and lymph nodes that are required for the most effective immune response. While there is ongoing controversy regarding the optimal dose and fractionation of RT required for anti-tumor immune responses, some preclinical data suggests that fractionated RT is more immunogenic and leads to increased immune mediated abscopal effects compared with large ablative doses of RT. Indeed in the mammary model described above where treatment with Flt-3 Ligand and RT led to growth delay of both irradiated and non-irradiated tumors, single doses of 2 Gy and 6 Gy were evaluated for ability to induce an abscopal effect. The study investigators found that 2 Gy and 6 Gy both led to tumor growth impairment, however there was no significant difference in the level of growth delay of the irradiated or non-irradiated tumors based on these two doses. This prompted the authors to conclude that “a single clinically relevant RT dose is unlikely to trigger an abscopal effect without the addition of FLT3-Ligand” and that “a low RT dose may be as effective as a higher dose in inducing the abscopal effect”. Indeed, in a phase I/II study evaluating *in situ* tumor vaccination with a Toll-like receptor 9 (TLR9) agonist and low dose fractionated radiation therapy in 2 Gy fractions in patients with low grade B-cell lymphoma, systemic clinical responses were detected. Fifteen patients with relapsed low grade B cell lymphoma (13 with FL and 2 with MZL) were treated with an *in situ* vaccination approach with an intra-tumoral Toll-like receptor 9 (TLR9) ligand coupled with low dose RT at the same tumor site to a dose of 4 Gy in 2 fractions over two consecutive days. The overall response rate in this small study was 27%, with one patient experiencing a complete response, three patients with partial response and stable disease observed in 8 patients. Taken together, these data suggest that radiation with standard fractionation of 2 Gy and at lower total radiation doses can be immunogenic and sufficient to support immune mediated, radiation induced distant tumor death. Radiation at ablative doses administered on a hypo-fractionated schedule are likely not required for eliciting an abscopal effect in radiosensitive tumor types, such as lymphoma.

We propose a phase II open label, unblinded single arm trial to evaluate the potential for fractionated radiation therapy to augment responses with PD-1 inhibitor Pembrolizumab. Among patients with progressive disease outside of the radiation therapy field after concurrent fractionated EBRT and pembrolizumab, a second course of EBRT administered on a hypo-fractionated schedule of at least 4 Gy per fraction with pembrolizumab will be evaluated. This approach will afford the ability to 1) assess the potential added efficacy of fractionated EBRT (as opposed to stereotactic body radiation therapy) to PD-1 immunotherapy in this refractory patient population 2) assess the ability of hypo-fractionated EBRT to offer salvage therapy to patients with progression after initial therapy with pembrolizumab and fractionated EBRT and

3) identify tumor and peripheral blood markers that correlate with response and/or toxicity based on serial specimens collected over the course of the trial.

The effect of external beam radiation therapy fractionation on radiation induced augmentation of immune checkpoint therapy is unclear. Most studies in solid tumors have utilized ablative stereotactic dose of RT. While we hypothesize that fractionated RT at 2 Gy per fraction will be effective for eliciting tumor responses (as supported by data stated above), it is plausible that hypo-fractionation is essential for synergy between checkpoint blockade immunotherapy and radiation. In an effort to identify the potential benefit of hypo-fractionation, among patients treated with standard fractionated EBRT and pembrolizumab that progress after combination therapy, we propose a second course of EBRT to be administered with a high dose per fraction, hypo-fractionated approach (of at least 4 Gy per fraction), to be administered with continued pembrolizumab therapy.

It is likely that the timing of immune checkpoint blockade and EBRT influence the effectiveness of therapy. In a pre-clinical model of melanoma, breast and colorectal cancer, the anti-tumor activity of low dose fractionated RT was enhanced through the combination of a monoclonal antibody targeting PD-L1. In this mouse model, treatment timing and scheduling was significantly affected treatment efficacy; with concurrent RT and PD-L1 therapy but not sequential therapy resulting in beneficial local control and survival. Based on these data we propose that pembrolizumab and fractionated RT should be administered concurrently.

The overall response rates of refractory NHL to single modality radiation therapy are relatively high but often not durable. In a retrospective study from the Dana-Farber Cancer Institute of 110 patients treated with a course of salvage radiation therapy for relapsed or refractory aggressive NHL, the overall response rate was 78% among refractory patients treated with curative intent and 81% for those refractory patients treated with palliative intent. Among living patients the 5 year rate of progression free survival however was only 34%. Furthermore even among patients treated with doses greater than 40 Gy with curative intent the 2 year local control rate was only 61%. This highlights 1) the need for effective systemic therapies to pair with salvage radiation therapy and 2) the room for improvement in long term local control that for patients with refractory NHL that may be accomplished with concurrent systemic therapy.

Given this data this study will address the role of pembrolizumab and concurrent RT in two patient populations. The first eligible cohort will include patients with more disseminated disease where all disease will not be included in the radiation field and there will be an “unirradiated lesion”. The second cohort of eligible patients will be those with relapsed/refractory aggressive NHL where all sites of disease can be encompassed in 1-2 radiation therapy fields. We hypothesize that 1) the response rates of the unirradiated lesion will be higher than reported ORR among patients treated previously with PD-1 blockade monotherapy for relapsed and refractory NHL and 2) the response rates for patients treated

with pembrolizumab and RT fields encompassing all sites of disease will be also be improved over rates reported for salvage RT alone.

An open-label Phase I trial (Protocol 001) was conducted to evaluate the safety and clinical activity of single agent MK-3475. The dose escalation portion of this trial evaluated three dose levels, 1 mg/kg, 3 mg/kg, and 10 mg/kg, administered every 2 weeks (Q2W) in subjects with advanced solid tumors. All three dose levels were well tolerated and no dose-limiting toxicities were observed. This first in human study of MK-3475 showed evidence of target engagement and objective evidence of tumor size reduction at all dose levels (1 mg/kg, 3 mg/kg and 10 mg/kg Q2W). No MTD has been identified to date. 10.0 mg/kg Q2W, the highest dose tested in PN001, will be the dose and schedule utilized in Cohorts A, B, C and D of this protocol to test for initial tumor activity. Recent data from other clinical studies within the MK-3475 program has shown that a lower dose of MK-3475 and a less frequent schedule may be sufficient for target engagement and clinical activity.

PK data analysis of MK-3475 administered Q2W and Q3W showed slow systemic clearance, limited volume of distribution, and a long half-life (refer to IB). Pharmacodynamic data (IL-2 release assay) suggested that peripheral target engagement is durable (>21 days). This early PK and pharmacodynamic data provides scientific rationale for testing a Q2W and Q3W dosing schedule.

A population pharmacokinetic analysis has been performed using serum concentration time data from 476 patients. Within the resulting population PK model, clearance and volume parameters of MK-3475 were found to be dependent on body weight. The relationship between clearance and body weight, with an allometric exponent of 0.59, is within the range observed for other antibodies and would support both body weight normalized dosing or a fixed dose across all body weights. MK-3475 has been found to have a wide therapeutic range based on the melanoma indication. The differences in exposure for a 200 mg fixed dose regimen relative to a 2 mg/kg Q3W body weight based regimen are anticipated to remain well within the established exposure margins of 0.5 – 5.0 for MK-3475 in the melanoma indication. The exposure margins are based on the notion of similar efficacy and safety in melanoma at 10 mg/kg Q3W vs. the proposed dose regimen of 2 mg/kg Q3W (i.e. 5-fold higher dose and exposure). The population PK evaluation revealed that there was no significant impact of tumor burden on exposure. In addition, exposure was similar between the NSCLC and melanoma indications. Therefore, there are no anticipated changes in exposure between different indication settings.

The rationale for further exploration of 2 mg/kg and comparable doses of pembrolizumab in solid tumors is based on: 1) similar efficacy and safety of pembrolizumab when dosed at either 2 mg/kg or 10 mg/kg Q3W in melanoma patients, 2) the flat exposure-response relationships of pembrolizumab for both efficacy and safety in the dose ranges of 2 mg/kg Q3W to 10 mg/kg Q3W, 3) the lack of effect of tumor burden or indication on distribution behavior of pembrolizumab (as assessed by the population PK model) and 4) the assumption that the dynamics of pembrolizumab target engagement will not vary meaningfully with tumor type.

The choice of the 200 mg Q3W as an appropriate dose for the switch to fixed dosing is based on simulations performed using the population PK model of pembrolizumab showing that the

fixed dose of 200 mg every 3 weeks will provide exposures that 1) are optimally consistent with those obtained with the 2 mg/kg dose every 3 weeks, 2) will maintain individual patient exposures in the exposure range established in melanoma as associated with maximal efficacy response and 3) will maintain individual patients exposure in the exposure range established in melanoma that are well tolerated and safe.

A fixed dose regimen of 200 mg of pembrolizumab administered every 21 days (q3weeks) is planned for this study. Available PK results in patients with NSCLC, melanoma, classical HL and other solid tumor types support a lack of meaningful difference in PK exposures obtained at a given dose among tumor types. A fixed dose regimen will simplify the dosing regimen to be more convenient for physicians and to reduce potential for dosing errors. A fixed dosing scheme will also reduce complexity in the logistical chain at treatment facilities and reduce wastage.

#### **4.2.2 Rationale for Endpoints**

The primary endpoint of this phase II trial is to determine the ORR for treatment with pembrolizumab and concurrent EBRT. For patients in Cohort 1 with multiple sites of relapsed or refractory disease, the ORR of an unirradiated lesion to pembrolizumab with EBRT will be determined. For Cohort 2 eligible patients all sites of radiographic lymphoma will be included in 1-2 RT fields and the ORR will be determined. Secondary endpoints include the determination of CRR, PFS, OS and duration of response of irradiated and non-irradiated lesions among patients treated with pembrolizumab with fractionated EBRT.

Disease response will be according to standard response criteria for NHL that was revised in 2014 (Appendix 11.3). For patients with FDG-avid disease, the Deauville Criteria will be utilized for PET-CT scoring on a 5 point scale, in accordance with standard response criteria. The 5 point scale is as follows, with score of 1-3 considered negative and 4-5 considered positive:

1. No uptake
2. Uptake less than or equal to the mediastinum
3. Uptake greater than the mediastinum but less than or equal to the liver
4. Moderately increased compared with the liver
5. Markedly increased compared with the liver
- X. New Areas of uptake unlikely to be related to lymphoma

While the immune related response criteria (irRC) are often utilized for immunotherapy trials, these criteria are best suited for assessing responses among patients with solid tumors and not in the setting of lymphoma. As we are interested in assessing the responses inside and outside of the irradiated field, in addition to determining overall response rates and overall complete response rates, we will also divide disease response into local (within the radiation field) and systemic (outside of the radiation field).

An ongoing challenge in assessing response to immunotherapy lies in the ability to distinguish true disease progression from immune induced inflammatory changes, i.e. pseudo-progression. Given that disease response may only become apparent radiographically following a

period of initial disease stability or progression, early evidence of clinically asymptomatic disease progression or new lesions detected in less than 3 months will not be criteria for study removal. While the first efficacy evaluation will occur at 8 weeks, if the study investigators suspect radiographic pseudo-progression in the absence of definitive clinical proof of disease progression, a subject may be granted an exception to continue on treatment until progression is confirmed at least 4 weeks later, provided that the subject's clinical condition is stable as detailed in Section 7.1.2.6.4.

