### **5.4 Radiation Therapy**

Radiation treatment will consist of definitive radiation therapy to a site of relapsed/refractory disease encompassed in one radiation therapy plan. Patients in Cohort 1 with relapsed or refractory lymphoma will be treated to one to two region(s) of disease with at least one distinct lesion excluded from the field and designated the “unirradiated lesion”. Patients in Cohort 2 with relapsed or refractory lymphoma will be treated with one to two RT plan(s) encompassing all sites of evident active disease. All patients (in both cohorts) will receive EBRT to a dose of 40-50 Gy in fractions sizes of 3 Gy or less. Integrated boost technique is permitted. Treatment will be administered 5 days per week, excluding holidays and weekends. For patients that are eligible for salvage hypo-fractionated EBRT, fraction sizes of at least 4 Gy will be used with a conformal delivery approach.

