#### **Radiation Target Volumes and Dosimetry**

- 1) Gross tumor volume (GTV) is defined as the tumor bulk visible radiographically on the CT planning scan.

2) The Clinical Target Volume (CTV) and Planning Target Volume (PTV) will be 5 -15 mm based on the type of image guidance utilized and the planned radiation technique. The prescription isodose line should cover greater than 98% of the GTV. We recommend PTV coverage of >95% when possible.

For patients enrolled in Cohort 1, the lesion(s) designated as the non-index lesion(s) outside of the radiation field should be at least 5 cm away from the radiation field. This lesion should be identified and documented prior to initiation of protocol therapy. In cases where the lesion is within 5 cm of the field, the non-index lesion(s) should be contoured and should receive a dose no greater than 5 Gy over the course of the entire radiation treatment.

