### **8.0 STATISTICAL ANALYSIS PLAN**

#### **8.1 Statistical Analysis Plan Summary**

This is an investigator initiated, open label, phase II clinical trial to evaluate the efficacy of the combination therapy of Pembrolizumab and fractionated external beam radiotherapy (EBRT) in patients with relapsed and refractory aggressive Non-Hodgkin lymphoma (NHL). The maximum number of patients that will be recruited for the study is 40.

The primary objective of the trial is to determine the overall response rate of Pembrolizumab and fractionated EBRT in patients with relapsed and refractory NHL. The secondary objectives are to evaluate the safety, CRR, PFS, OS and duration of response of pembrolizumab with concurrent fractionated EBRT. Patients will receive 200 mg IV of Pembrolizumab with concurrent EBRT at standard of care doses of 40-50 Gy of EBRT in fractions of  $\leq 3$  Gy.. The trial enrollment will be stratified according to the extent of relapsed/refractory disease included in the RT field(s) with 2 cohorts of patients enrolled based on the treated RT field. For Cohort 1, patients with aggressive NHL, will receive RT to 1-2 region(s) of disease and the ORR will be determined for a designated “unirradiated” lesion (Cohort 1). For patients with relapsed/refractory aggressive NHL in Cohort 2, RT will be administered to encompass all sites of radiographically evident disease in 1-2 RT plan(s), the ORR will be based on the disease treated within the RT field. **The maximum number of patients in each cohort is 20 with a total anticipated trial enrollment of 40 patients..**

Overall response rates to PD-1 blockade monotherapy among patients with hematologic malignancies is based on published data. For cohort 1, we assume that concurrent external beam radiation therapy with concurrent pembrolizumab will improve ORR (of the non-irradiated lesion[s]) over the reported rates of PD-1 blockade which are roughly 26% for B cell lymphoma and 17% for T cell lymphoma.

**While the ORR for definitive RT for patients with de novo aggressive NHL approach 100%, overall response rate to salvage RT for patients with refractory aggressive NHL treated with curative intent has been reported to be 78%, with a 5 year progression free survival rate of 34%. We assume that concurrent EBRT and pembrolizumab will improve the ORR when all sites of known disease are radiated.**

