#### **8.2 Statistical Analysis Plan**

Phase II design:

The overall response (OR: complete response + partial response) of non-irradiated lesion(s) at three months and dose limiting toxicity (DLT) at one cycles (3 weeks) will be monitored simultaneously using the Bayesian stopping boundaries calculated based on beta-binomial distributions. Independence is assumed between OR and DLT.

DLT is defined as the following toxicities observed during cycle one of the treatment that are considered by the investigator to be related to therapy:

1. Grade 4 neutropenia (ANC < 500/mm3) lasting more than 7 consecutive days.
2. Grade 3 neutropenia with fever and/or infection, where fever is defined as an oral Temperature  $\geq 38.5^{\circ}\text{C}$ .
3. Grade 4 thrombocytopenia (platelets < 25,000/mm3) lasting more than 7 consecutive Days.
4. Grade 3 thrombocytopenia with clinically significant bleeding.
5. A platelet count < 10,000/mm3 at any time.
6. Grade 3 or greater nausea and/or emesis despite the use of optimal anti-emetic Prophylaxis. Optimal anti-emetic prophylaxis is defined as an anti-emetic regimen that employs a 5-HT3 antagonist given in standard doses and according to standard schedules.
7. Grade 3 or greater diarrhea that occurs despite maximal supportive therapy.
8. Any other Grade 3 or greater non-hematologic toxicity with the following exceptions: Grade 3 arthralgia/myalgia or brief (< 1 week) Grade 3 fatigue.
9. A delay of more than 2 weeks in the initiation of Cycle 2 of treatment because of a lack of adequate recovery of therapy related hematological or non-hematologic toxicities.

In cohort 1 for the patients with multiple sites of aggressive NHL, we will consider that the regimen is promising if the OR rate of the non-irradiated lesion (s) at 3 months is at least 35% and the DLT rate at cycle one is below 30%. A sample size of 20 ensures that, if the trial is not terminated early, a posterior 90% credibility interval for OR rate at 3 months will have width of 0.335 at most, when 7 responses are observed out of the 20 patients, under the assumption of 35% OR rate. The prior probability of OR and DLT for the regimen are modeled by beta distribution ( $\text{Beta}(0.35, 0.65)$  and  $\text{Beta}(0.3, 0.7)$ , respectively). Denoting the probability of OR and DLT by  $\{\theta_{\text{OR}}, \theta_{\text{DLT}}\}$ , and they are compared to fixed targets of OR and DLT rates. The following decision criteria will be applied:

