### 11.3 Recommendations for Initial Evaluation, Staging, and Response Assessment of Hodgkin and Non-Hodgkin Lymphoma: The Lugano Classification

The Lugano Classification will be used in this study for assessment of tumor response. While either CT or MRI may be utilized, for FDG avid tumors, PET-CT is the preferred imaging technique in this study.

Table 3. Revised Criteria for Response Assessment		
Response and Site	PET-CT-Based Response	CT-Based Response
Complete	Complete metabolic response	Complete radiologic response (all of the following)
Lymph nodes and extralymphatic sites	Score 1, 2, or 3* with or without a residual mass on 5PS† It is recognized that in Waldeyer's ring or extranodal sites with high physiologic uptake or with activation within spleen or marrow (eg, with chemotherapy or myeloid colony-stimulating factors), uptake may be greater than normal mediastinum and/or liver. In this circumstance, complete metabolic response may be inferred if uptake at sites of initial involvement is no greater than surrounding normal tissue even if the tissue has high physiologic uptake	Target nodes/nodal masses must regress to $\leq 1.5$ cm in LD i No extralymphatic sites of disease
Nonmeasured lesion	Not applicable	Absent
Organ enlargement	Not applicable	Regress to normal
New lesions	None	None
Bone marrow	No evidence of FDG-avid disease in marrow	Normal by morphology; if indeterminate, IHC negative
Partial	Partial metabolic response	Partial remission (all of the following)
Lymph nodes and extralymphatic sites	Score 4 or 5† with reduced uptake compared with baseline and residual mass(es) of any size At interim, these findings suggest responding disease At end of treatment, these findings indicate residual disease	$\geq 50\%$ decrease in SPD of up to 6 target measurable nodes and extranodal sites When a lesion is too small to measure on CT, assign 5 mm $\times$ 5 mm as the default value When no longer visible, 0 $\times$ 0 mm For a node $> 5$ mm $\times$ 5 mm, but smaller than normal, use actual measurement for calculation Absent/normal, regressed, but no increase Spleen must have regressed by $> 50\%$ in length beyond normal
Nonmeasured lesions	Not applicable	None
Organ enlargement	Not applicable	Not applicable
New lesions	None	

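### The Cohort 1 primary endpoint does not say whether one designated unirradiated lesion or all out-of-field disease is scored, yet its rate is set against a patient-level response rate

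*Combined protocol and SAP*

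**What the plan says.** **Singular wording.** Section 4.2.2 states that for Cohort 1 "the ORR of an unirradiated lesion to pembrolizumab with EBRT will be determined". Section 8.1 states that "the ORR will be determined for a designated" unirradiated lesion.

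**Wording that allows several.** Section 2.1 (primary objective) and section 3.1 (hypothesis) refer to lesion(s) or lesions. Section 8.2 gives the criterion: "we will consider that the regimen is promising if the OR rate of the non-irradiated lesion (s) at 3 months is at least 35" percent. Section 8.1 itself uses the optional plural in its comparison sentence.

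**How the lesion is fixed.** Section 5.4 asks for "at least one distinct lesion excluded from the field and designated the" unirradiated lesion. Under Radiation Target Volumes and Dosimetry the plan adds: "This lesion should be identified and documented prior to initiation of protocol therapy". It sets a 5 cm distance, or a 5 Gy limit for closer lesions. It does not say which lesion to designate when there are several, how many are scored, or who selects.

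**The benchmark.** Section 8.1 assumes that adding radiation "will improve ORR (of the non-irradiated lesion[s]) over the reported rates of PD-1 blockade which are roughly 26% for B cell lymphoma", with 17% for T-cell lymphoma. Section 4.2.1 sets the response of the unirradiated lesion against the response rate reported among patients. Its Figure 3 shows that these are patient counts: 8 of 31 and 4 of 23.

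**The response criteria.** Section 11.3 adopts the Lugano classification, which is a whole-patient scale. Its CT-based partial response needs a 50% or greater "decrease in SPD of up to 6 target measurable nodes and extranodal sites". Its PET-based partial response uses the five-point score with reduced uptake and has no six-lesion sum. Both allow no new lesions. Progression can rest on a single node or a single new lesion.

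**A related category.** Section 4.2.2 and the Efficacy Endpoints text also split response into local (in field) and systemic (out of field), but do not name the systemic response as primary.

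**The concern.** Section 4.2.1 describes Cohort 1 as the more disseminated group and section 4.2.2 refers to multiple sites, so some patients can be expected to have more than one lesion outside the field.

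Take a patient whose designated lesion shrinks to a partial response while another unirradiated node meets the Lugano threshold for progression. Under the singular wording this patient is a responder. Under Lugano applied to all out-of-field disease, the same patient has progressive disease. Two analysts following the plan could classify the patient differently.

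Cohort 1 asks whether radiation raises the out-of-field response above that of PD-1 blockade alone. If the numerator is scored on one lesion and the benchmark on whole patients, part or all of an apparent gain may come from the change of unit. The benchmark and the target are only 35% − 26% = 9 points apart for B-cell disease, and the cohort has 20 patients, so modest discordance matters.

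**Working it through.** **1. The plan's own figures reproduce (section 8.2).** With the Beta(0.35, 0.65) prior and 7/20 responses, the posterior is Beta(7.35, 13.65). Its equal-tailed 90% interval is 0.191 to 0.526, width 0.335 as stated. At 10 patients, P(OR rate < 0.35) is 0.971 with 1 response and 0.865 with 2, so the rule stops at 0–1, as tabulated. Early stopping is 1 − [1 − P(X ≤ 1 | 10, OR)] × P(Y ≤ 5 | 10, DLT). At OR 0.35 and DLT 0.1 this gives 0.0861, as stated. The design arithmetic is sound; the open question is what counts as a response.

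**2. Effect of scoring one lesion.** Let π be the true patient-level rate and q the net share of patient-level non-responders whose designated lesion responds. It is net of any patient-level responders whose designated lesion does not respond. The documents give no value for q, so it is an assumption shown over a range. Then

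single-lesion rate = π + (1 − π) × q.

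With π = 0.26, meaning no gain over the B-cell benchmark:

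| q (assumed) | Single-lesion rate | P(at least 7/20) | P(0–1 of 10), futility stop |
|---|---|---|---|
| 0 | 0.260 | 0.247 | 0.222 |
| 5% | 0.26 + 0.74 × 0.05 = 0.297 | 0.381 | 0.154 |
| 10% | 0.26 + 0.74 × 0.10 = 0.334 | 0.523 | 0.103 |
| 12.2% | 0.350 | 0.583 | 0.086 |

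Both probabilities are exact binomial. Seven of 20 is used because it is the observed 35% mark in section 8.2; the plan states no formal success rule at 20 patients. P(at least 7/20) ignores the interim look. Requiring at least 2/10 first changes it little: 0.242 instead of 0.247 at a rate of 0.26, and 0.576 instead of 0.583 at 0.35.

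**3. Discordance needed to reach 35% with no gain.** q = (0.35 − π)/(1 − π). From 26%: 0.09/0.74 = 12.2%. From 17%: 0.18/0.83 = 21.7%.

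**4. Lower limit.** A patient with one unirradiated lesion has no second lesion to disagree with it, so on lesion choice that patient contributes nothing to q. If every patient had one, the gap would be zero.

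**The case against.** **An all-lesion reading is available.** The objective, the hypothesis and the decision criterion all allow the plural, Lugano is the stated scale, and an out-of-field category is already planned. This stands: the plan is ambiguous. A reader might infer a fixed one-lesion rule, which the documents taken together do not support. But the singular wording is also there, and no section settles which applies.

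**Cherry-picking is not shown.** A reader might infer that the investigator picks a favourable lesion. No section names who selects, and documentation before therapy excludes choosing after the response is seen. Choice on baseline features remains possible, and pre-specification does not remove the mismatch of units.

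**Large inflation is not shown.** A reader might treat 26% as the rate at which all of 2–3 lesions respond, with an assumed within-patient correlation of 0.3–0.7. That gives single-lesion rates of 33–52% and a 48–96% chance of at least 7/20 (with at least 2/10 at the interim look). The documents give neither lesion counts nor correlations, and requiring every lesion to respond is stricter than Lugano. Nor is the six-lesion sum the general rule: it belongs to the CT column, while PET-CT is preferred for FDG-avid disease.

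**26% is not a formal null.** The stopping rule uses a fixed 35%. The 26% also pools histologies (Figure 3: DLBCL 36%, FL 40%, other B-cell 0%), while section 5.1.2 excludes indolent B-cell lymphoma. This stands, but sections 4.2.1 and 8.1 still name the published rates as those to be improved on.

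**Secondary endpoints help.** Response of irradiated and non-irradiated lesions, PFS and duration of response would reveal growth elsewhere. They do not change how the primary response or the interim count is scored.

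**Conclusion.** The concern holds as an unresolved definition with a consequence. The Cohort 1 primary endpoint is worded both for one designated lesion and for several. No rule combines several lesions or accounts for progression elsewhere outside the field, and the single-lesion wording gives a rate that is not like-for-like with the patient-level benchmark.

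The size is conditional. An assumed net discordance of 12.2% would by itself turn a true 26% into the 35% target, more than double the chance of seeing 7/20 (0.247 to 0.583), and cut the chance of a futility stop from 0.222 to 0.086. At 5% the shift is smaller but visible. The documents do not show how common discordance is, so they do not support a claim that pembrolizumab alone would probably reach 35%. The matter should be corrected, with medium confidence in its practical size.

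**What to change.** In sections 4.2.2, 8.1 and 8.2, define Cohort 1 overall response in the same words, for example:

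*Out-of-field (systemic) complete or partial response at 3 months by Lugano over all unirradiated disease, using PET-CT criteria for FDG-avid disease and otherwise CT criteria with up to six target lesions recorded before Day 1; no progression of any other unirradiated lesion and no new lesion outside the field.*

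Reconcile this wording with the pseudo-progression and confirmation text in sections 4.2.2, 7.1.2.6.3 and 7.1.2.6.4, so that the SAP states how progression still awaiting confirmation counts in the 3-month response. Keep the designated-lesion response as a secondary, descriptive abscopal measure.

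**Cost.** Wording changes and a baseline record of out-of-field lesions. The response scans are already scheduled (section 6.1, footnote o) and the out-of-field split is already planned. The Cohort 1 rate will be somewhat lower and early futility stops correspondingly more likely: for example, 0.222 at a true 26%, against 0.086 if single-lesion scoring had lifted that to 35%.
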